## 11. MEDICATIONS

### 11.1 Concomitant Medication

All medications will be coded using the World Health Organization Drug Dictionary (WHO-DD) Version B2 enhanced March 2018. Prior and concomitant medications will be summarized by treatment group and by the number and percentage of participants taking each medication, classified by using WHO-DD Anatomical Therapeutic Chemical Level 3 and preferred term.

Prior medications are defined as medications or therapies initiated prior to the start of the study drug and terminating prior to the start of study drug. Hence, these medications or therapies will have end dates prior to the first dose date of study drug. Concomitant medications are defined as any medications other than the study drug that a participant receives concurrently with the study drug. These medications will have end dates on or after the first dose date of the study drug until ten days after last dose date.

Prior and Concomitant medications will be summarized. All medications will be presented in a listing.

Participants' Lifetime Prior Psychiatric Medications (i.e., discontinued  $\geq$  60 days prior to the Screening visit) will also be summarized by treatment group and by the number and percentage of participants taking each medication, classified by using WHO-DD Anatomical Therapeutic Chemical Level 3 and preferred term.

Please refer to [Section 7.3](#) for the conventions used to impute partial start dates and end dates of concomitant medications.

### 11.2 Exposure and Compliance

The treatment duration will be calculated as (number of days=last dose date - first dose date+1) and summarized. Participants that are lost to follow up or have a missing last dose date will be assigned a last dose date of the day before the last attended clinic visit for analysis purposes.

All pill count shortage (negative pill count) of greater than 4 doses (8 tablets) per 4-week assessment period and/or any between-visit compliance  $<70\%$  will be considered protocol deviations, and the reason for the pill count discrepancy will be discussed with the participant and documented in the CRF to ensure that any cases of potential abuse or misuse are identified. Participants with more than one significant incidence of negative pill count discrepancy during the double-blind phase of the study will be closely monitored by the investigator.

Exposure will be measured using the last date of treatment and first date of treatment. Total exposure will be defined as the last date of treatment minus the first date of treatment plus one. The number of participants with total exposure by visit weeks ( $\leq 4$  weeks (study Day 0 to 28), 4 to  $\leq 8$  (study Day 29 to 56), 8 to  $\leq 12$  (study Day 57 to 84) and  $> 12$  weeks (study Day  $\geq 85$ )) will be presented. Additionally, exposure days, defined as the total number of tablets taken divided by 2 (and rounded up to the nearest whole number), will be summarized.

Compliance will similarly be summarized across all study visits for each treatment arm. Study drug compliance as a percentage will be defined as the number of pills taken by the participant divided by the total number of pills that the participant was assigned to take multiplied by 100.

For calculating the compliance and exposure days, the following convention will be applied: for periods where drug is issued, but the participant does not return any bottles or tablets, or the participant misses the visit entirely, that period will not contribute to the compliance or exposure calculation unless the bottles are returned at a later visit.

Compliance will be summarized with descriptive statistics by treatment arm. The number and percentages of participants within certain categories of compliance e.g. < 50%, 50% to < 70%, 70% to  $\leq$  100%, greater than 100% will be presented. Compliance between 70% to 114% will not be considered a protocol deviation. Tablet counts, calculation of compliance overall and by visit, which bottles of study drug were returned at each visit, and participant-reported reasons for all tablet discrepancies at all visits will be presented in a listing.

In addition, participants with significant over-usage or otherwise unaccounted-for missing tablets resulting in >114% compliance for any visit (e.g., failure to return >8 tablets per 4 week interval) will be summarized by visit and overall. These listings will include both the participant-reported reason for the discrepancy plus the investigator's assessment of potential abuse, misuse or diversion. Tables will be created for higher level abuse-related MedDRA terms as listed in [Appendix 4](#). Additional terms may be identified and included; note that somnolence is an anticipated drug effect and would only be considered indicative of potential abuse in the presence of other indicators of substance abuse. Clinically significant drug accountability discrepancies associated with missing medication, loss of drug, or cases in which the PI confirms concern over drug abuse, misuse or diversion, will be examined and discussed in the CSR.

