9.2. Dosing Instructions

Patients will be instructed to take two tablets of their assigned study drug (TNX-102 SL 2.8 mg tablets or placebo tablets) sublingually, placed simultaneously under the tongue, each evening at bedtime starting at bedtime on evening of Day 1 (Day of Visit 2) and continuing without interruption for 12 weeks. The study drug should be taken at bedtime after teeth brushing and other oral care has been completed. The mouth/sublingual area should be moist at the time of dosing, so the patient should drink a few sips of water prior to dosing, especially if prone to dry mouth. Patients will be instructed to place the two SL tablets under their tongue and keep them there until they have dissolved. They should not swallow, crush or chew the tablets. Patients should not eat or drink (or chew gum) for at least 15 minutes after dosing, and preferably not until morning. Patients will be reminded that only 2 (two) tablets are allowed per day. Note: In the event that the patient misses a dose, instruct the patient to continue dosing with two (2) tablets the next evening; i.e., they should not take more to make up for the missed dose.

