10.3. Visit 3 (Telephone Visit: Day 14)

Visit 3 will be done as a telephone call to the patient and should be conducted after 2 weeks of treatment, on Day 14 ± 3 days.

The following steps should be completed:

- Assess changes in concomitant medications
- Assess study drug compliance based on patient verbal report
- Assess occurrence of adverse events, including any oral adverse events and whether an unscheduled visit is indicated for an examination of the oral cavity
- Review patient instructions regarding drug dosing.
- Administer the ‘Since Last Visit’ C-SSRS

After all of the items have been reviewed with the patient, the patient should be given an appointment to return to the clinic for Visit 4, and be re-instructed, as necessary, on dosing instructions, and reminded to bring study medication back to the clinic at their next visit.

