## 6. ANALYSIS POPULATIONS

The following analysis populations are planned for this study:

- **Safety Population (SAFETY):** All participants who receive at least 1 dose of study drug. Participants who are issued study drug, but return 100% of it (i.e., none consumed) will be excluded from the safety population; likewise, participants that have no follow up following receipt of study drug to indicate they took drug are excluded. All safety analyses and demographic/baseline characterization will be performed using this population, analyzed as treated; participants will be summarized under TNX-102 SL 5.6 mg if they were issued it at any visit.
- **Modified Intention-to-Treat Population (mITT):** All randomized participants who have at least a baseline and one post-baseline CAPS-5 assessment. This is the primary population for efficacy analyses and participants will be analyzed based on their randomized treatment.

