### 10.1 Adverse Events

All AEs, treatment-emergent adverse events (TEAEs), and SAEs will be coded using MedDRA, version 21.0.

TEAEs are defined as either new onset AEs with an onset at the time of or following the start of treatment through ten days after the last dose of study medication, or a recurrence of an AE (or medical history) present prior to randomization but increasing in severity, frequency or relationship at the time of or following the start of treatment

An AE summary table will be presented for the following:

- TEAEs by severity

- TEAEs leading to study drug discontinuation
- TEAEs by relationship
- SAEs
- Oral Cavity AEs

Summaries of incidence rates (frequencies and percentages) of individual AEs by MedDRA SOC and preferred term will be prepared. Such summaries will be displayed for all TEAEs, TEAEs by maximum severity, and TEAEs by strongest relationship to study drug.

Each participant will be counted only once within each summation level (SOC; preferred term). If a participant experiences more than one TEAE within each summation level only, the TEAE with the strongest relationship or the maximum severity, as appropriate, will be included in the summaries of relationship and severity.

Additionally, a summary of the Oral Cavity AE characteristics will be presented; this includes information such as temporal proximity to the dose, duration and whether the AE was present the following morning.

Adverse events of special interest pertaining to abuse potential (as defined in the January 2017 Assessment of Abuse Potential for Drugs – Guidance for Industry) will be analyzed separately by treatment group, SOC and preferred term, and displayed in tabular format.

In the AE data listings, all AEs will be displayed. AEs that are treatment-emergent will be flagged.

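### SAP 11.2 ignores the Week 2 call when imputing the last dose date, so a patient lost after it gets 0 days of treatment; SAP 10.1 and 7.3.1 disagree on whether that date limits treatment-emergent events

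*SAP*

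**What the plan says.** **Last dose and duration.** The SAP 11.2 rule covers "Participants that are lost to follow up or have a missing last dose date"; each of these "will be assigned a last dose date of the day before the last attended clinic visit". Treatment duration is then "number of days=last dose date - first dose date+1". For tablet-based exposure days, the same section leaves out any period for which no bottles or tablets come back.

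**Visits.** Protocol 9.2 has dosing "starting at bedtime on evening of Day 1 (Day of Visit 2"). Protocol 10.3 says: "Visit 3 will be done as a telephone call to the patient and should be conducted after 2 weeks of treatment, on Day 14 ± 3". At that call the site is told to "Assess study drug compliance based on patient verbal report" and to ask about adverse events. The next scheduled clinic visit is Visit 4, on Day 28 ± 5 (Protocol 10.4).

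**Safety population.** SAP 6 removes only those with nothing to show that drug was taken: "participants that have no follow up following receipt of study drug to indicate they took drug are excluded". A patient who reports dosing at the call therefore stays in.

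**Treatment-emergent events.** There are three statements:
- SAP 10.1 counts new-onset events from the start of treatment "through ten days after the last dose of study medication".
- SAP 7.3.1 sorts events into pre-treatment and treatment-emergent by one CRF item, which asks whether onset preceded the first dose.
- Protocol 12.1 counts events that begin once treatment has started and gives no end date.

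SAP 12 reports no departure from the protocol.

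**The concern.** The imputation rule looks only at visits made in person, yet the one scheduled contact in the first four weeks of treatment is by telephone. A patient can confirm nightly dosing at that call, be kept in the Safety population because of it, and still be given a last dose that precedes the first.

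These patients have no post-baseline CAPS-5, because the first is at Visit 4. They are therefore outside the mITT population, and the safety outputs are where their treatment experience is reported. Safety is the secondary objective. The treatment-duration summary would carry an impossible value for them. The same date also enters two other definitions: the end of the treatment-emergent window in SAP 10.1 and the end of the concomitant-medication window in SAP 11.1.

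The word joining the two conditions in SAP 11.2 is *or*. Read literally, a lost patient's last dose date is replaced even when one was recorded.

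**Working it through.** The plan states no figure of its own on this point, so the check applies the SAP's rules to calendar dates.

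**Inputs**
- First dose date F: the evening of Visit 2 (Protocol 9.2).
- Study-day convention (SAP 7.1): F is Day 1, the day before is Day −1, and there is no Day 0.
- Visit 3 call on Day c, with c from 11 to 17 (14 ± 3, Protocol 10.3).
- The patient has no clinic, unscheduled or early termination visit after Visit 2.

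**Imputed last dose.** L = Visit 2 − 1 = F − 1, which is Day −1, before the first dose.

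**Treatment duration.** L − F + 1 = (F − 1) − F + 1 = 0 days. If the first dose was taken one day after Visit 2, then L = F − 2 and the duration is −1.

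**What the call can document.** With dosing from Day 1 to the night before the call, the duration is c − 1, that is 10, 13 or 16 days for a call on Day 11, 14 or 17.

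**Tablet-based exposure days.** No bottles are returned, so the period does not contribute. This measure does not repair the duration.

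**Treatment-emergent window under SAP 10.1, if the imputed date is used.** L + 10 = F + 9 = Day 10. An event reported at the call must have started by Day c, so the onsets left outside are Days 11 to c. With the call counted, the last dose is Day c − 1 and the window ends on Day c + 9.

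| Call on | Duration, SAP 11.2 rule | Duration, call counted | 10.1 window ends, SAP 11.2 date | Reported onsets outside it | 10.1 window ends, call counted |
|---|---|---|---|---|---|
| Day 11 | 0 | 10 | Day 10 | Day 11 | Day 20 |
| Day 14 | 0 | 13 | Day 10 | Days 11–14 | Day 23 |
| Day 17 | 0 | 16 | Day 10 | Days 11–17 | Day 26 |

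**Under SAP 7.3.1 or Protocol 12.1.** The last dose date is not used, so none of these onsets is lost, whatever date is imputed.

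**Concomitant medication.** SAP 11.1 ends its window ten days after the last dose date, which is again Day 10 here.

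**Exposure category.** Durations of 0 and of 10–16 days both fall in the SAP 11.2 class of up to 4 weeks.

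**The case against.** The strongest reply is that the practical effect is small, and much of it stands. The exposure category is the same either way, so only the continuous duration summary must change. All adverse events are listed whatever their status (SAP 10.1), and the serious adverse event table in SAP 10.1.2 is not limited to treatment-emergent events. A patient who attends an early termination or unscheduled clinic visit escapes the problem. A lost patient will seldom have a recorded last dose date to overwrite, although the wording would overwrite one.

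Four stronger readings are tempting and are not supported:
- *Events on Days 11–17 lose treatment-emergent status.* A reader might infer this from SAP 10.1 alone. SAP 7.3.1 and Protocol 12.1 both keep those events, and SAP 10.1 does not say that the date imputed in 11.2 feeds its window. Even under 10.1, the full range applies only to a call on Day 17, and onsets up to Day 10 are kept.
- *Patients lost after Visit 4 are also cut short because they left with two new bottles.* Dispensed tablets show supply, not dosing. If Visit 4 was the last contact, the remedy below gives the same date as the present rule.
- *Tolerability problems concentrate in these losses.* SAP 7.1.3.1 has patients who leave because of adverse events coded to that reason, not as lost to follow-up. The documents do not show how many lost patients had such problems.
- *A count of affected patients can be given.* The documents contain no rate of loss between Visits 3 and 4.

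The reply leaves two things unanswered: a stated rule that yields a last dose before the first, and two SAP sections that can classify the same event differently.

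**Conclusion.** The point holds in two parts of different strength.

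**Certain.** Followed literally, SAP 11.2 gives 0 days of treatment to a patient whose last contact is the Visit 3 call, against about 10–16 days that the call may document. This assumes that the first dose was taken on the day of Visit 2, that dosing was reported up to the night before the call, and that no later in-person visit took place. The rule as worded also overrides a recorded last dose date for a lost patient.

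**Conditional.** SAP 10.1 conflicts with SAP 7.3.1 and Protocol 12.1 on when treatment-emergent status ends. If 10.1 governs and takes the imputed date, the window closes on Day 10, and new-onset events from Day 11 to the day of the call are excluded. Under either of the other two rules, none is. The concomitant-medication window in SAP 11.1 has the same dependence on the last dose date.

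The effect is on the duration summary and, conditionally, on the treatment-emergent and concomitant-medication tables. The efficacy analyses are not touched. The text should be corrected before database lock because it produces an impossible date and the repair is cheap.

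**What to change.** 1. **SAP 11.2.** Use the recorded last dose date whenever there is one, including for patients lost to follow-up. Where there is none, use the day before the latest contact of any type at which dosing was reported, with Visit 3 counted. Never assign a date earlier than the first dose.
2. **SAP 10.1 and 7.3.1.** Reconcile the two so that one rule defines treatment-emergent events and the window is never closed on an imputed last dose date. If an upper limit is kept for recorded dates, list it in SAP 12 as a departure from Protocol 12.1.
3. **SAP 11.1.** State which last dose date ends the concomitant-medication window, and apply the same approach to imputed dates.

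The cost is a few lines of SAP text and programming. The Visit 3 information is already collected. Treatment-emergent counts may rise slightly.

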9. STUDY DRUG MATERIALS AND MANAGEMENT

9.1. Study Drug Packaging, and Labeling and Storage

Study drug supplies will be packaged identically so as to maintain the integrity of the study blind. The study medication bottles will be labeled minimally with the following information: study number TNX-CY-P302, sponsor name and address, bottle number, quantity, storage conditions, usage instructions, and caution statements for investigational new drug, i.e., Caution: New Drug – Limited by United States Law to Investigational Use, and Keep Out of Reach of Children and Pets.

Each study medication bottle will contain 40 tablets. Two bottles will be dispensed to each patient at Visit 2 (baseline), Visit 4 (Week 4), and Visit 5 (Week 8); this will provide the patient with 80 tablets to cover the 4 weeks of dosing between visits, plus additional tablets to cover loss and/or visit window variability. The patient should be instructed to take all the tablets in one bottle before opening the second bottle. The patient should be instructed to keep this study medication in a safe location out of extreme environmental conditions and out of the reach of children and pets, and be instructed that this medication is not to be taken by any individual other than the study patient. Each patient will also be instructed that they will be expected to return both bottles and all unused study medication at each clinic visit; unused medication will be counted to assess compliance with study drug treatment.

Storage of the study drug at the investigational site should be under locked and secure conditions with limited staff access. Study drug should be stored at 20-25°C/68-77°F in a temperature/humidity-monitored room; however, brief excursions (15-30°C/59-86°F) as defined in the Study Reference Manual (IP Receipt and Storage) are permitted without the sponsor's approval.

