9.5. Study Drug Accountability and Reconciliation

All patients will be expected to bring their bottles of study medication with them to all study visits. At each study visit, the site staff will inspect the medication bottles, and perform a count of the tablets remaining in the bottles and document this in the patient’s record. An assessment of medication adherence should be done by the study staff to ensure that the patient understands all dosing instructions and is taking the medication as prescribed. Patients will be asked for an explanation if the count of returned study drug tablets indicates a discrepancy between the expected number of tablets dosed and the number returned in the bottles. If it is found that the patient is not taking the study medication as expected, the patient will be re-c counseled with instructions, and this should be noted in the patients’ records. A deviation should be recorded on any patient who is less than 70% compliant with dosing between visits.

If the patient fails to return any of the unused study drug as expected, the patient should be questioned regarding the reason for the lower than expected tablet number and about potential misuse, abuse or diversion. If more than 8 tablets cannot be accounted for at any of the visits where drug is returned (Week 4, 8 and 12), the investigator will be asked to evaluate the situation, and a written summary of this evaluation should be added to the source and entered onto the case report form (CRF). Situations where replacement drug is requested, or when more than 8 tablets cannot be accounted for, should be recorded as deviations.

All study medication, including partial and empty bottles, must be maintained at the study site until Tonix or its designee verifies drug accountability and provides instruction for destruction or the return of the investigational product to the Sponsor’s drug distribution depot.

Tonix or their designee will perform drug accountability which entails reconciliation between the amount of drug shipped to the study site, study drug assigned and dispensed to the patient (including returned unused assigned study drug), and study supplies that were never dispensed and/or assigned to patients.

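### A complete non-return of study drug has no compliance value, so it cannot meet the >114% trigger of the SAP's over-use and missing-tablet summary

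*SAP*

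**What the plan says.** SAP section 11.2 (Exposure and Compliance) contains all the main pieces.

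- **Definition.** Percentage compliance is "the number of pills taken by the participant divided by the total number of pills that the participant was assigned to take multiplied by 100".
- **Exclusion.** Where drug was issued but "the participant does not return any bottles or tablets, or the participant misses the visit entirely", the convention is that "that period will not contribute to the compliance or exposure calculation unless the bottles are returned at a later visit". It governs percentage compliance and the tablet-based exposure days.
- **Summary of over-use and missing tablets.** This is tabulated by visit and overall for participants with over-use or "unaccounted-for missing tablets resulting in >114% compliance for any visit". The example in brackets is failure to return more than 8 tablets per 4-week interval. The output carries the investigator's view on abuse, misuse or diversion.
- **Deviation limits.** A pill-count shortage of more than 8 tablets per 4-week period is a protocol deviation. Later in the same section: "Compliance between 70% to 114% will not be considered a protocol deviation".

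The protocol works in tablets, not percentages. Section 9.5 makes more than 8 unaccounted-for tablets a deviation. It also asks for a written investigator evaluation: "If more than 8 tablets cannot be accounted for at any of the visits" at which drug is returned. On supply, section 9.1 says of the two bottles that "this will provide the patient with 80 tablets to cover the 4 weeks of dosing between visits", and section 9.2 fixes use at two a day: "Patients will be reminded that only 2 (two) tablets are allowed per day".

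**The concern.** The exclusion and the trigger work against each other. A period with no compliance value cannot exceed 114%, so a participant who brings back nothing cannot qualify for the summary, while a participant who brings back most of the surplus can. The bracketed example points the other way, since returning nothing is a failure to return more than 8 tablets. Two programmers could read the section differently and produce different counts.

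At stake is the descriptive table meant to show, by visit and overall, how much drug went missing or was over-used. Under the literal trigger, that table counts moderate shortfalls and leaves out complete non-returns. The documents give no non-return rate, so the number of participants affected cannot be estimated.

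A second, smaller problem is that the section uses 114% and 8 tablets as if they were the same limit. They are not, and one sentence clears as a non-deviation what another can call a deviation.

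**Working it through.** **Inputs**

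- Issued per period: 2 bottles × 40 = 80 tablets (protocol 9.1).
- Assigned: 2 per day (protocol 9.2), so 2 × 28 = 56 in 28 days.
- Compliance = tablets taken / tablets assigned × 100 (SAP 11.2). Tablets that do not come back count as taken when a count exists.
- Visit windows (protocol 10.4 and 10.5): Visit 4 on Days 23–33, Visit 5 on Days 51–61, Visit 6 on Days 79–91.

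**The plan's own figure.** (56 + 8)/56 = 64/56 = 114.29%. The stated 114% is the 8-tablet rule at 28 days, rounded down.

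**Who enters the summary at 28 days**

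| Case | Tablets gone | Compliance | Meets >114%? |
|---|---|---|---|
| 10-tablet shortfall | 66 | 66/56 = 117.9% | Yes |
| Both bottles returned empty | 80 | 80/56 = 142.9% | Yes |
| Nothing returned | up to 80; at least 80 − 56 = 24 beyond those assigned | none | No |

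The 24 tablets are three times the 8-tablet limit. If the non-return were counted with all 80 tablets gone, it would score 142.9%, the same as the empty bottles.

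**Effect on overall compliance.** Take a participant with 56 tablets used in each of two periods and nothing returned in the third. With that period dropped, overall compliance is 112/112 = 100.0%. With it counted as 80 gone, it is 192/168 = 114.3%.

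**114% against 8 tablets.** Assume that the denominator is 2 × actual days, d. An excess of x tablets passes 114% when x/(2d) > 0.14.

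- Eight tablets stay at or below 114% only if 8/(2d) ≤ 0.14, which needs d ≥ 29.
- Nine tablets pass 114% only if 9/(2d) > 0.14, which needs d ≤ 32.
- The two rules therefore agree for every shortfall at 29–32 days.
- At 28 days, 8 tablets give 114.29%: above 114%, but not more than 8.
- At 33 days, 9 tablets give (66 + 9)/66 = 113.6%. At 35 days they give (70 + 9)/70 = 112.9%. Both are more than 8 tablets, yet inside the 70–114% band.

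Dispense-to-return intervals can run from 18 days (Day 33 to Day 51) to 40 days (Day 51 to Day 91).

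**Limit of any excess-based rule.** At 36 days, 80 − 72 = 8, which is not more than 8, and 80/72 = 111.1%. From 36 days on, without replacement supply, a complete loss passes neither limit. At 38 days it is 80/76 = 105.3%, and at 40 days 80/80 = 100%. Non-return therefore needs its own row even after the trigger is corrected.

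**The case against.** A reader might infer that complete non-return escapes detection altogether. The documents do not support that.

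- The deviation rule for more than 8 missing tablets (SAP 11.2, protocol 9.5) is a tablet count and needs no percentage. SAP 8.2 summarises deviations by type and by arm.
- Protocol 9.5 has patients who fail to return unused drug questioned about misuse, abuse or diversion.
- SAP 11.2 lists the bottles returned at each visit with reasons for discrepancies, and has clinically significant missing or lost drug discussed in the study report.

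A reader might also infer that the largest losses are the ones missed. That is not so either. Two empty bottles represent the same 80 tablets gone, and they are counted at 142.9%. Bottles returned late are counted too. The gap depends on whether the containers come back, not on the size of the loss.

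Nor is exposure lost as a whole. Total exposure is defined by first and last dose dates and is untouched; only the tablet-based exposure days drop the period.

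It can further be said that leaving unknown counts out of a percentage is sound practice, that the bracketed example already covers non-return, and that the 33–35 day cases rest on a denominator the SAP does not spell out. All three are fair.

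What remains is narrow. The stated trigger and its example give opposite answers for a complete non-return. The parallel routes do not supply the same table: deviations are grouped by type, listings are not counts, and the study report discussion depends on a judgement of clinical significance. The written evaluation in protocol 9.5 is tied to visits where drug is returned. That phrase may simply name the scheduled visits, but its reach to a visit with no return is unclear.

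**Conclusion.** The inconsistency stands, and it is minor. As worded, a period with nothing returned cannot enter the over-use and missing-tablet summary, although at 28 days it leaves at least 24 tablets unaccounted for and a 10-tablet shortfall does enter. The consequence is limited to this one descriptive output and to tablet-based exposure days. The primary efficacy analysis is not affected.

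The mismatch between 114% and 8 tablets is also real but small. The 28-day discrepancy follows directly from the documents' figures. The discrepancy at 33–35 days assumes that tablets assigned means two per actual day in the interval. If the SAP intends a fixed 56 per period, that part falls away and only the rounding at 64/56 remains.

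**What to change.** In SAP section 11.2:

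1. Define the missing-tablet summary by the number of unaccounted-for tablets, more than 8 per interval, and state that it does not depend on the compliance exclusion.
2. Add a separate row for no drug returned, by arm and visit, split into visit attended and visit missed or lost to follow-up. The split keeps routine dropouts out of the abuse and diversion flag, where the expected count is in any case undefined.
3. Keep the exclusion convention for percentage compliance only.
4. State whether tablets assigned means two per actual day or a fixed number per period.
5. Reconcile the sentence on 70–114% compliance with the 8-tablet deviation rule in SAP 11.2 and protocol 9.5.

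The cost is SAP wording and one derived variable from tablet counts already collected. More participants may appear in the table. Some will be innocent losses, and the separate row makes those easier to read.
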